4.1. **Include statistical power calculations and the assumptions made in making these calculations.** The following power calculations for Aims 1-3 assume the availability of 86 subjects who are eligible for randomization into one of two groups (n=43 per group). We assume a range of intra-class correlation of 0.1-0.5 and up to 10 follow-up measures per participant. The sample size is inflated to accommodate a 30% missing or dropout rate by 6 months based on rates over a similar period of time in previous studies⁵⁵. We consider a conservative adjustment in the two-sided level of significance, 0.025, to account for two hypothesis tests per Aim (3-month and 6-month outcome). Table 4 presents the detectable effect size based on the above assumptions for 90% and 80% power. The study will have 80% power to detect a moderate effect size of 0.50 standard deviations of a continuous outcome measure at 6 months assuming an intra-class correlation of 0.3. Table 5 presents the detectable effect in units applicable to each outcome based on the observed standard deviation from studies in the literature.

Power	Intra-class Correlation	Detectable effect size	
		3 months	6 months
80%	0.1	0.35	0.40
	0.3	0.48	0.50
	0.5	0.58	0.61
90%	0.1	0.40	0.41
	0.3	0.55	0.57
	0.5	0.66	0.70

(Assumptions: power=80%; n=30 per group after 30% attrition; 2-sided=0.05)

- Standard Deviation
- Insomnia Se
- Quality of Life
- Pooled within group standard deviation
- Pooled within group standard deviation (estimated from presented data)
- Pooled within group standard deviation for general health

Outcome	Pre-Post S.D. ^a	Detectable Difference
ISI ^b	3.809 ^d	1.90 points
Abstinent Days	15.96 ^e	7.98 %
Health Related QOL ^c	9.15 ^f	4.58 points

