model. In this model, the mean ISI depends on fixed covariates and random effects⁵⁷. The fixed covariates of interest include time, treatment assignment, the interaction between time and treatment assignment, adjusting for family history of alcoholism and confounding variables identified in the preliminary analysis. The random effects represent the unobserved factors that lead to variation of the individual participant's outcome. Random intercepts for each participant permit modeling of natural variation across participants at baseline in the outcome of interest. In addition, random slopes or random effects for the trajectory of each participant over time allow for variation of each participant about a mean, overall trajectory across all participants. Estimates of the random effect for an individual participant also permit far more focused investigations of those individuals who depart from the mean over time and experience either better or worse than average change in outcome. Thus, the mixed effects longitudinal model permits both comparisons of groups as well as contrasts of individuals. Although less robust to model misspecification, the mixed effects paradigm offers special flexibility in longitudinal data when exposures vary over time and when dropout and missed visits lead to unbalanced groups. ISI and quality of life are continuous measures and most likely follow a symmetric or approximately normal distribution. Therefore the linear mixed regression model is appropriate. If departures from normality are found, we will consider transformations or other distributional forms that may better fit the data. The alcoholism-related outcome measures are counts (e.g. number of days abstinent, number of heavy drinking days, etc.) but will be summarized as percentages (e.g. percent abstinent days) and will also most likely follow a normal distribution. The target of inference is the participant-specific response to treatment over time. Specifically we are interested in the efficacy at the end of treatment (8 weeks) and durability after 3 and 6 months of follow-up. At each time point of interest, we will estimate from the fitted model the difference from baseline in the outcome for each treatment group and test the difference between these differences. The treatment effects will be the contrasts that represent the difference of differences from baseline in outcome across treatment groups at 3 and 6 months. Both univariate and multivariate results will be reported in terms of Wald test, point estimates, and 95% confidence intervals.

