
Exploratory Aim 4: We will examine whether family history of alcoholism modifies the effect of the intervention on outcomes. Effect modification or moderators of the intervention will be tested and estimated with 3- and 2-way interactions among the treatment factor, potential moderator, and time in the ITT models described above. Because the hypotheses relating to effect modification will be exploratory, we will use $p=0.1$ to declare significance of such interactions. The analyses will be followed with stratified analyses corresponding to the effect modification hypotheses.

Regarding missing data and drop-out, we will assess the relationship of missing data patterns with dependent and independent variables. Specifically, we will use logistic regression with missingness as the binary outcome and dependent and independent variables under each Aim as covariates for the missing data model. If there are significant associations, we will perform multiple imputations with PROC MI in SAS, and take weighted averages of parameter estimates and standard errors from the longitudinal regressions across the multiple imputation iterations.

W. Privacy and Confidentiality

1. **Indicate the type of data that will be received by the Principal Investigator. Check all that apply.**

- 1.1. De-identified – Without any identifiers that could link the data to a specific participant. (Contact Privacy Officer for assistance. If data is coded, it is not considered de-identified.)

- 1.2. Identified – Linked to a specific participant by identifiers sufficient to identify participants. (See HIPAA and Common Rule Criteria for list of identifiers.)
- 1.3. Coded – Linked to a specific subject by a code rather than a direct identifier. If coded is checked, specify:

1.3.1 **Explain who will maintain the link or code.** The principal investigator and the research assistant will have access to the codes, which will be stored in a locked filing cabinet in room #228 or in the locked cabinet in [name] office (TBA). In addition, the code will also be stored in a back-up file in the password protected online drive of the principal investigator on the MIRECC drive (\\vhaphifpcmirecc\Research Studies\[name] – CBT-I) or the K: drive of the PI\vhaphiclunas11s (K:).

1.3.2 **Describe who will have access to the link or code.** P.I., and/or the study coordinator.

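### If multiple imputation is used, the plan's pooling rule averages standard errors and so leaves out between-imputation variance

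*Combined protocol and SAP*

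**What the plan says.** The missing-data paragraph closes Section V item 4.2. Missingness is first modelled: "we will use logistic regression with missingness as the binary outcome and dependent and independent variables under each Aim as covariates". Imputation depends on the result: "If there are significant associations, we will perform multiple imputations with PROC MI in SAS". The results are then pooled as follows: "take weighted averages of parameter estimates and standard errors from the longitudinal regressions across the multiple imputation iterations".

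This is the only combining rule in the documents. They give no weights, number of imputations, between-imputation term or reference distribution. PROC MI, the one procedure named, creates the imputed data sets and does not pool results. The text does not say whether imputed results replace the mixed model on observed data or supplement it.

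Two other places bear on the point. For Aims 1-3, item 4.2 says: "Both univariate and multivariate results will be reported in terms of Wald test, point estimates, and 95% confidence intervals". In item 4.1 the power calculation uses a "conservative adjustment in the two-sided level of significance, 0.025, to account for two hypothesis tests per Aim", and "The sample size is inflated to accommodate a 30% missing or dropout rate by 6 months".

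**The concern.** Each imputed data set yields an estimate and a standard error computed as if the imputed values had been observed. The uncertainty about those values shows up in how far the estimates differ from one imputation to the next. An average of the standard errors has no term for that spread, whatever the weights, so the pooled standard error treats imputed values as real data.

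The Wald statistic and the confidence interval both use this standard error directly. In the imputation branch the treatment contrasts would therefore look more precise than they are. That branch is entered when missingness is related to study variables, which is when sound inference matters most.

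**Working it through.** **Inputs from the plan.** Item 4.1 has 43 per group randomized, "n=30 per group after 30% attrition", an intra-class correlation (ICC) of 0.1 to 0.5, up to 10 follow-up measures, and a detectable 0.50 SD at 6 months with 80% power at ICC 0.3. The text uses two-sided 0.025.

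**The plan's own figure.** Take the SD of a mean of m measures as sqrt((1 + (m−1) × 0.3)/m). With a difference of 0.50, two-sided 0.025 and 80% power, m = 8 to 10 requires 30 to 29 per group. Power at 30 per group is 0.81 to 0.83. Then 30/0.7 = 42.9, or 43 per group and 86 in total. The sample size reproduces, and the pooling rule does not affect it.

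**Pooling formula.** Let W be the mean within-imputation variance, B the variance of the estimates across M imputations, and T the total variance:

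- T = W + (1 + 1/M)B
- λ = (1 + 1/M)B/T, the share of total variance due to missing data

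The equal-weight average of the standard errors is at most sqrt(W), so its ratio to the correct value is at most sqrt(W/T) = sqrt(1−λ). Unequal weights only move the result between the smallest and largest per-imputation standard errors; they add no term for B. The direction of the error therefore needs no assumed input. Only its size does.

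**Size.** True error = 2 × (1 − Φ(z × sqrt(1−λ))), with z = 2.241 for 0.025 and 1.960 for 0.05. For example, at λ = 0.2: sqrt(0.8) = 0.894, 2.241 × 0.894 = 2.005, and the error is 0.045. The values of λ are assumptions; M is taken as large.

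| λ (assumed) | SE ratio | SE too small by | Error at nominal 2.5% | Error at nominal 5% | Coverage of 95% interval |
|---|---|---|---|---|---|
| 0.05 | 0.975 | 2.5% | 2.9% | 5.6% | 94.4% |
| 0.1 | 0.949 | 5% | 3.35% | 6.3% | 93.7% |
| 0.2 | 0.894 | 11% | 4.50% | 8.0% | 92.0% |
| 0.3 | 0.837 | 16% | 6.08% | 10.1% | 89.9% |
| 0.4 | 0.775 | 23% | 8.25% | 12.9% | 87.1% |

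A small M makes it worse. With W = 1−f, B = f and M = 5, the error at nominal 2.5% is 3.5 / 4.9 / 6.9 / 9.5% for f = 0.1 / 0.2 / 0.3 / 0.4.

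**Which λ is plausible.** Two simulations used 43 per arm, about 30% missing at 6 months, ICC 0.1 / 0.3 / 0.5 and the difference in change from baseline at 6 months.

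- *Four time points, monotone dropout at random, M = 20, 3,000 runs per ICC.* λ was 0.21 to 0.24. At ICC 0.3 the mean averaged standard error was 0.257, the empirical value 0.291, and the value with B included 0.294. Rejection at nominal 2.5% was 4.7 to 5.4% with averaged standard errors and 2.6 to 2.9% with B included (normal reference). At nominal 5% it was 7.8 to 8.8% against 5.0 to 5.4%.
- *Missingness depending on the baseline score, 0 / 15 / 30% missing at 3 months, M = 10, 2,000 runs per cell.* The fraction of missing information was 0.21 to 0.27 and the averaged standard error was 11 to 15% too small. Rejection at nominal 2.5% was 4.5 to 6.5% against 1.8 to 2.6% by Rubin's rules. At nominal 5% it was 7.1 to 10.7% against 4.1 to 5.1%. Monte Carlo error is about 0.3 to 0.7 points per cell, so the direction and rough size are supported but not the decimals.

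**The case against.** The strongest reply is that this is loose wording in a short summary, not a choice of method. Standard pooling gives each imputation equal weight, so the word 'weighted' already suggests imprecision, and a statistician using PROC MI may well go on to the standard combining step. That is possible. But the sentence names standard errors as a quantity to be averaged, and nothing elsewhere corrects it. If the standard rules were intended, the correction changes no result.

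The other objections limit the reach of the point, and they stand as limits:

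- Imputation is conditional. If it is not triggered, the mixed model on observed data stands and the error does not arise. If imputed results only supplement that model, the main tests are unaffected.
- The 0.025 level appears as a power assumption. A table note in item 4.1 gives two-sided 0.05, and the analysis text sets no test level. Results are therefore shown at both levels.
- The simulations used simpler models than the planned one with up to ten follow-ups. An analytic check with baseline plus ten follow-ups, exchangeable correlation and no random slopes put the 6-month fraction at about 0.18 to 0.29, or roughly 4 to 6% error at nominal 2.5%. The 0.4 row is thus beyond what 30% missing supports. At 3 months, with time as categorical, the fraction ran from 0 to about 0.22, or 2.5 to 4.8% error, depending on when dropout occurs.
- Missingness may fall below 30%. Phone or mailed assessments (Section N, Data Collection, items 2.1.1 and 2.1.2) and follow-up after stopping therapy (Section S, item 1) are planned. The bias then shrinks but does not reverse.

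**Conclusion.** The concern holds. As written, the pooling rule is wrong and not merely incomplete, and its standard errors are too small whenever the estimates vary between imputations. With 30% missing at 6 months and an assumed fraction of missing information of 0.2 to 0.3, the understatement is about 11 to 16%. Error at a nominal 2.5% is then about 4.5 to 6.1%, roughly double, and nominal 95% intervals cover about 92 to 90%. These sizes rest on assumed values of the fraction and of M. The effect is confined to the imputation branch. It should be fixed before the analysis is run.

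**What to change.** Replace the pooling clause with wording such as: 'Estimates will be combined by Rubin's rules (PROC MIANALYZE). The pooled estimate is the mean across the M imputations; its variance is the mean within-imputation variance plus (1 + 1/M) times the between-imputation variance, with the corresponding t reference distribution.' State M.

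It would also help, though it is not part of this error, to say whether imputed results replace or supplement the mixed model on observed data.

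The cost is one sentence in the plan and one standard SAS procedure. Design, sample size and data collection do not change. Intervals will be somewhat wider, and correct, when imputation is used.
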